## Summary of Inclusion Exclusion Criteria

To be enrolled in this study, participants must have the following characteristics:

- Veteran
- Be current cigarette smokers of at least ten cigarettes a day.
- Meet criteria for current PTSD.
- Speak and write fluent conversational English.
- Be between 18 and 75 years of age.
- Be willing to attempt smoking cessation.

Potential participants will be excluded from participating in this study for the following reasons:

- Screened participants will not be stable on their medications for the study period
- Screened participants who have a history of myocardial infarction in the past 6 months
- Screened participants who have a contraindication to NRT and are unable to get medical clearance from their primary care provider will be excluded.

- Screened participants who use any other forms of tobacco such as cigars, pipes, or chewing tobacco and are unwilling to stop using.
- Pregnancy
- Inability to complete study measures and tasks independently
- Dementia or other brain disorder, schizophrenia, current manic syndrome, or substance abuse/dependence in the preceding 3 months.
- Currently receiving trauma-focused psychotherapy.
- Currently enrolled in another smoking cessation trial.
- Currently living in court-ordered residential substance abuse treatment.

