### Assessments After Screening

Prior to each session, participants will complete questionnaires to assess psychiatric symptoms and smoking variables. These include the PTSD checklist (PCL), questions about smoking behavior in the past week, and the Beck Depression Inventory (BDI-II). In the final two sessions, participants will also complete the ASI, QOLI, TRGI, PSQI-A, CAPS, treatment satisfaction, Cook Medley Hostility Scale, e-cigarette use measure, and a question about current non-study psychotherapy. In session 8, participants will complete measures of treatment credibility and expectancy using the Reaction to Treatment Questionnaire (Borkovec & Nau, 1972). At the beginning and end of treatment, therapists will rate their level of allegiance to the therapy they are using with a single question asking "Which treatment do you think leads to better outcomes?" In the final treatment session, participants will also complete measures of SmokeFreeVet usability, and the nicotine dependence stages of change measure. In session 14 (after the final treatment session), participants will be interviewed with the CAPS.

Abstinence and relapse will be monitored by ED entries and at visits 7-14. Participants will provide breath samples for carbon monoxide (CO) analysis at every laboratory visit following their quit date. The first verification of smoking abstinence will occur on the morning following their quit date. Smoking abstinence will be obtained by self-report and verified by comparing CO levels to the level obtained at the baseline visit. The chart below lists the sliding scale of CO values that will be considered validating. At the six month follow-up visit, salivary cotinine will also be used to confirm self-reported

smoking abstinence. The formula in Table 1 below uses the participant's CO reading at the screening visit to determine the threshold that will be considered as confirming smoking abstinence after the quit date for each participant.

Table 1. Carbon Monoxide Thresholds for Validating Smoking Abstinence			
CO SCREENING	AM CO LIMIT		
		AM CO Limit after Overnight	
14-15	15	Abstinence	
16-18	16	AM CO Limit Formula: [14 + (.25 *	
19-21	17	(1.33 * (SCREENCO -14)))]	
22-24	18		
25-27	19		
28-30	20		
31-33	21		
34-36	22		
37-39	23		
40-42	24		
43-45	25		
46-48	26		
49-51	27		
52-54	28		
55-57	29		
58-60	30		
61-63	31		
64-66	32		
67	33		

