# Nicotine Replacement Therapy

All participants will receive nicotine replacement therapy in session 6, and will be asked to begin using NRT on their quit date (just prior to session 7). Participants will be provided with detailed information and education regarding the use of the nicotine skin patches. This educational component will include a rationale for using the patches, proper placement of the patch, when to use them, possible side effects, and how to report side effects to research staff as they may occur in the course of the study. All participants will also be given the option of one NRT rescue method of their choosing (nicotine gum, lozenges or inhalers).

Medications will be distributed under the consultation of study physician, [name]., Ph.D. [name] prescribes smoking cessation pharmacotherapy for the Durham VA specialty smoking cessation clinic. [name] is familiar with standard smoking cessation pharmacotherapy and side effects. He will determine initial nicotine dosage levels and consult on any adjustments to medication dosage. For example, patients only smoking 10 cigarettes a day would likely not benefit from 21mg/day nicotine patches, and will begin NRT at 14mg/day. Recent research has suggested that for heavy smokers (i.e., smokers with CO readings higher than 30 ppm), smoking cessation efficacy is greater when high dose (42 mg) nicotine patches are used in the pre-cessation phase (Rose, personal communication; Rose, 2010). The side effect profile for heavy smokers using a 42 mg patch is low. Rose (personal communication) reports that 2.5% of heavy smokers using a 42 mg. patch pre-quit report vomiting (as compared to 0.4% with the 21 mg. patch). No other adverse effects were reported. Smokers in this study were allowed to use their usual brand of cigarettes. Taken together, these studies suggest that pretreatment with nicotine patch while smoking cigarettes is safe and tolerable.

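### At low screening CO, the Table 1 abstinence limit is not below the participant's own smoking-level reading, so CO cannot refute a false report of quitting

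*Combined protocol and SAP*

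**What the plan says.** Under Assessments After Screening, the rule is: "Smoking abstinence will be obtained by self-report and verified by comparing CO levels to the level obtained at the baseline visit". CO is taken at every laboratory visit after the quit date. On the limit itself, the section says: "The formula in Table 1 below uses the participant's CO reading at the screening visit to determine the threshold".

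Table 1 has rows for screening CO from 14 to 67 ppm. Its first two rows set a limit of 15 for 14–15 and 16 for 16–18; its last sets 33 for 67. The formula beside the rows opens "AM CO Limit Formula: [14 + (.25" and continues "1.33 * (SCREENCO -14", that is, 14 + 0.25 × 1.33 × (screening CO − 14). The limit is labelled as a morning value after overnight abstinence. The text does not say whether a CO equal to the limit passes, or what applies below 14 ppm.

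The smoking criterion for entry is "Be current cigarette smokers of at least ten cigarettes a day"; no CO minimum is listed. The Nicotine Replacement Therapy section discusses participants at that floor ("patients only smoking 10 cigarettes a day would likely not benefit from 21mg/day nicotine patches"), so they are expected.

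Salivary cotinine, with a cut point of 10 ng/ml, is added as confirmation at the six-month visit only. In the data analysis section, the main Hypothesis 3 analysis uses abstinence at Week 6; six months is secondary.

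**The concern.** Biochemical verification exists to contradict a false report of quitting. It can do so only if the limit lies below the level the participant shows while smoking. If the limit equals or exceeds that level, someone who has changed nothing meets it, even on the first morning after the quit date.

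At stake is mainly the Week-6 abstinence rate. Hypothesis 3 sets that rate against published VA usual-care data and regresses abstinence on group. False reports that pass the CO check would raise the rate relative to the published figures. If equally common in both arms, they would dilute the arm contrast. Cotinine could not readily stand in at Week 6: the protocol describes it as a metabolite of nicotine, and nicotine replacement runs until six weeks after the target quit date.

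**Working it through.** **Inputs.** The printed rows and formula of Table 1, and the absence of a CO minimum in the inclusion and exclusion criteria. Write S for screening CO in ppm.

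**Formula.** Limit = 14 + 0.25 × 1.33 × (S − 14) = 14 + 0.3325 × (S − 14).

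**Where the formula limit is not below S.** Limit − S = (1 − 0.3325) × (14 − S) = 0.6675 × (14 − S). This is zero at S = 14, positive below 14 and negative above 14.

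| S | Printed limit | Formula | Printed − S | Formula − S |
|---|---|---|---|---|
| 8 | none | 12.005 | – | +4.005 |
| 10 | none | 12.67 | – | +2.67 |
| 13 | none | 13.6675 | – | +0.6675 |
| 14 | 15 | 14.00 | +1 | 0 |
| 15 | 15 | 14.3325 | 0 | −0.6675 |
| 16 | 16 | 14.665 | 0 | −1.335 |
| 17 | 16 | 14.9975 | −1 | −2.0025 |
| 18 | 16 | 15.33 | −2 | −2.67 |
| 67 | 33 | 31.6225 | −34 | −35.3775 |

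**Do the rows reproduce the formula?** No. Over the 54 whole values from 14 to 67, the printed limit exceeds the unrounded formula every time, by up to 33 − 31.6225 = 1.3775 ppm (at 67). Rounding the formula to the nearest whole number, or down, matches 0 of 54 rows; rounding up matches 18. Rounding to nearest and adding 1 matches all 54. The rows may therefore show the first failing value, in which case CO must be strictly below the limit. The text does not say so.

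**When does an unchanged CO pass?**
- Printed rows, equality passes: S = 14, 15 and 16.
- Printed rows, CO must be below the limit: within the table, S = 14 only (14 is below 15). At 15 and 16 a fall of 1 ppm is enough.
- Unrounded formula, equality passes: S = 14 and, if extended, everything below. At 15 and 16 a whole-number reading of 14 passes, a fall of 1 or 2 ppm.

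By contrast, at S = 67 the printed limit is 33/67 = 0.49 of the screening value, so a fall of about half is needed.

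**The case against.** Several parts of the case against this point stand.

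- **The 16 ppm boundary is not firm.** It rests on the printed rows with equality passing. The protocol says the formula sets the threshold, and the formula gives 14 or below. The section's description of the chart values as validating, and the column label of limit, favor letting equality pass but do not settle it. On every reading, however, a change of at most 2 ppm is enough at 14 to 16.
- **Below 14 the plan prints no limit.** The values 12.67 and 12.005 come from extending the formula below its own anchor. That is a natural reading, since the threshold is said to be set for each participant. If it is rejected, these participants have no verification rule at all.
- **A false self-report is also needed.** A reader might infer that low-CO participants are verified while still smoking. The documents support only that they can be, because CO is added to self-reported abstinence and does not replace it.
- **The Week-6 outcome is not stated to be CO-verified.** A reader might infer that these participants count as biochemically verified in Hypothesis 3. The analysis section says only that they are abstinent. Electronic diaries also monitor smoking, but they are self-report too.
- **The ten-a-day remark concerns patch dose** and says nothing about CO. It shows who may enroll, not what their readings will be.

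**Conclusion.** The point holds in a limited form. The CO limit is not below the participant's own screening value at 14 to 16 ppm on the printed rows (equality passing), or at 14 ppm and below on the formula (equality passing at 14 itself, extended below it). Entry criteria do not keep such participants out. For them, CO cannot refute a false report of abstinence, and no other biochemical check is described until six months. Separately, and without any assumption, the printed rows and the formula disagree at every tabulated value.

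The number affected is unknown. Purely as an illustration, if 10% to 30% of 50 to 70 participants screened at 16 ppm or below (an assumption), that would be 0.10 × 50 = 5 to 0.30 × 70 = 21 people. This counts those for whom the check may have little or no force, not those misclassified; the latter also requires false reports, whose frequency the documents do not give. The effect on Hypothesis 3 depends on whether Week-6 abstinence is meant to be CO-verified.

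**What to change.** 1. Reconcile the rows of Table 1 with the formula, state which governs, and state whether a CO equal to the limit passes.
2. State the rule for screening values below 14 and above 67 ppm.
3. Where the resulting limit is not below the participant's own screening CO, require a limit below that reading, or classify the participant as not CO-verifiable and say in advance how such participants are counted. Leave the other rows unchanged.
4. State whether Week-6 abstinence requires CO verification.
5. Report Week-6 abstinence with and without participants screened at 16 ppm or below, a cut that covers every reading of the rule.

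A broader remedy, such as capping every limit at half the screening CO, goes further than the defect: it would lower 47 of the 54 tabulated limits (at 30 ppm, from 20 to 15), and nothing in the documents supports that.

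The cost is a clarified table, a sentence in the analysis section, and rescoring of CO values already collected at screening and post-quit visits. The downside is that a few true quitters with low screening CO may fail verification or be left out of the sensitivity analysis.

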Heavy smokers (as defined by CO readings greater than 30 ppm) will be prescribed 42 mg. patches. Two weeks after their quit date, participants will lower the dose of the prescribed nicotine patch (i.e., participants receiving 21 mg initially will lower to 14 mg, and those receiving 42 mg will lower to 21 mg). At three weeks after the quit date, any participant who initially received the 42 mg patch will lower the patch dose further to 14 mg. At four weeks post-quit, all participants will replace the 14 mg patch with a 7 mg patch, to be worn for two weeks. All NRT, including both the patch and rescue method, will end 6 weeks after the target quit-smoking date. If any participant has been unable to maintain abstinence during the follow-up period, he/she may be allowed to reinitiate NRT during the follow-up period in order to make a renewed quit attempt. Dosage of NRT will be decided by the study physician at this time point, and will depend upon the participant's most recent smoking patterns and CO reading.

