9	
 
CPT 8 + Relapse         Prevention/Renewed         Quit Attempt
 
Verify Smoking         Abstinence
 
Questionnaires
 
Step down to 21 or 14         mg patch NRT + rescue         method
 
	
 
Smoking treatment 8
 
Verify Smoking Abstinence
 
Questionnaires
 
Step down to 21 or 14 mg patch NRT + rescue method
 
	\$20 visit

Session	Tasks		Payment
	1 hr, 45 min	55 min	
10	
 
CPT 9 Relapse         Prevention/Renewed         Quit Attempt
 
Verify Smoking         Abstinence
 
Questionnaires
 
Continue or step down         to 14 mg patch NRT +         rescue method     
 
1 hr, 45 min
 
	
 
Smoking treatment 9
 
Verify Smoking Abstinence
 
Questionnaires
 
Step down to 21 or 14 mg patch NRT + rescue method
 
	\$20 visit
11	
 
CPT 10 + Relapse         Prevention/Renewed         Quit Attempt
 
Verify Smoking         Abstinence
 
Questionnaires
 
Step down to 7mg patch         NRT + rescue method
 
	
 
Smoking treatment 10
 
Verify Smoking Abstinence
 
Questionnaires
 
Step down to 7mg patch NRT + rescue method
 
	\$20 visit
	1 hr, 45 min	55 min	
12	
 
CPT 11 + Relapse         Prevention/Renewed         Quit Attempt
 
Verify Smoking         Abstinence
 
Questionnaires
 
Continue 7mg patch         NRT + rescue method
 
	
 
Smoking treatment 11
 
Verify Smoking Abstinence
 
Questionnaires
 
Continue 7mg patch NRT + rescue method
 
	\$20 visit
13	
 
1 hr, 45 min
 
CPT 12 + Relapse         Prevention/Renewed         Quit Attempt
 
Verify Smoking         Abstinence
 
Questionnaires
 
End of NRT
 
Continue bupropion
 
Weight measurement
 
Begin 1 week of EMA
 
	
 
Smoking treatment 12
 
Verify Smoking Abstinence
 
Questionnaires
 
End of NRT
 
Continue bupropion
 
Weight measurement
 
Begin 1 week of EMA data collection
 
	\$20 visit

Session	Tasks		Payment
	data collection		
	1 hr, 15 min	30 min	
14	
 
End EMA data collection; Return study equipment
 
Verify Smoking Abstinence
 
CAPS
 
		\$20 visit; \$25 for EMA; \$25 incentive pay; \$35 equipment return
	60 min		

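### Table 1's overnight CO limit, which depends only on screening CO, is the only CO threshold for validating abstinence and is applied at every visit after the quit date

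*Combined protocol and SAP*

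**What the plan says.** The rule is in Assessments After Screening: "Smoking abstinence will be obtained by self-report and verified by comparing CO levels to the level obtained at the baseline visit". On timing: "Participants will provide breath samples for carbon monoxide (CO) analysis at every laboratory visit following their quit date", and "The first verification of smoking abstinence will occur on the morning following their quit date". On the limit: "The chart below lists the sliding scale of CO values that will be considered validating", with the Table 1 formula using screening CO "to determine the threshold that will be considered as confirming smoking abstinence after the quit date for each participant".

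Table 1 carries the label "AM CO Limit after Overnight" (the word for abstinence follows in the next cell). The printed formula is 14 + (0.25 × (1.33 × (SCREENCO − 14))). The tabulated limits run from 15 at screening CO 14–15 to 33 at screening CO 67.

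Table 2 lists "Verify Smoking Abstinence" at each of sessions 8 to 15. Salivary cotinine, cut at 10 ng/ml, is added at the six-month visit only. The same section names 7- and 30-day point prevalence abstinence, at each assessment, as secondary smoking outcomes.

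Under Hypothesis 3, abstinence at Week-6 is the main outcome and six-month cessation is secondary. The one other CO threshold is in Nicotine Replacement Therapy, where readings above 30 ppm define heavy smokers. It has nothing to do with validating abstinence.

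**The concern.** By its own label, Table 1 describes the CO level to accept on the morning after one night without smoking. That fits the first check. The text then applies the limit to abstinence after the quit date with no end point, and nothing replaces it at later visits. The only variable in the formula is screening CO, so the limit is the same on the first morning and at six months.

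Two sets of outcomes are at stake. The 7- and 30-day outcomes cannot be verified by a limit built to be met after one night: someone who smoked until the previous evening is the very person it is designed to pass. The Week-6 outcome of Hypothesis 3 probably relies on the same limit. Before the six-month visit CO is the only biochemical check planned, so until then nothing else tests the self-report.

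**Working it through.** **Inputs.** Table 1 and its formula, the verification text and the 7- and 30-day definitions (Assessments After Screening); the visit list (Table 2); the 30 ppm heavy-smoker cut and the end of NRT (Nicotine Replacement Therapy); the entry criteria; Hypothesis 3 (Data Analysis and Hypotheses).

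**1. Reproducing Table 1.** With S the screening CO, f(S) = 14 + 0.25 × 1.33 × (S − 14) = 14 + 0.3325 × (S − 14). At each of the 54 whole-number values from 14 to 67, the printed limit equals the rounded formula plus 1 ppm. For example, f(30) = 14 + 0.3325 × 16 = 19.32, which rounds to 19; the table prints 20. The plan does not say whether a reading equal to the limit passes. If the printed limit is exclusive, table and rounded formula agree throughout.

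**2. Highest whole-number reading that confirms abstinence.** There are three ways to read the rule: table inclusive, table exclusive, or the unrounded formula with readings at or below it passing.

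| Screening CO | f(S) | Table, inclusive | Table, exclusive | Formula | Smallest fall that confirms |
|---|---|---|---|---|---|
| 14 | 14.00 | 15 | 14 | 14 | none |
| 30 | 19.32 | 20 | 19 | 19 | 33–37% |
| 40 | 22.65 | 24 | 23 | 22 | 40–45% |
| 60 | 29.30 | 30 | 29 | 29 | 50–52% |
| 67 | 31.62 | 33 | 32 | 31 | 51–54% |

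The fall is (S − highest confirmed reading) / S; at S = 30, (30 − 20)/30 = 33% and (30 − 19)/30 = 37%. The inclusive table exceeds the whole-number part of the formula by 1 ppm at 19 values and by 2 ppm at 35, so the picture does not depend on the inequality.

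**3. Against the plan's own heavy-smoker cut.** A reading of 31 ppm meets the definition of a heavy smoker (above 30 ppm). It also confirms abstinence from screening CO 61 (table inclusive), 64 (table exclusive) or 66 (formula).

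**4. Visits governed.** Table 2 lists verification at eight sessions, 8 to 15. It lists none at session 7, the scheduled quit date, and shows no morning-after check. The one check that the label fits is therefore missing from the schedule.

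**5. Whether Week-6 is included.** Hypothesis 3 gives no origin for Week-6 and does not mention CO. Nicotine Replacement Therapy says "All NRT, including both the patch and rescue method, will end 6 weeks after the target quit-smoking date", and Table 2 puts the end of NRT at session 13, where verification is also listed. Counted from the quit date, Week-6 is therefore session 13. Counted from the first treatment session it would be treatment session 6, which is study session 7; Table 1 would then fit and only later visits would be affected.

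**6. Ends of the table.** Entry requires at least ten cigarettes a day but sets no CO range, and Table 1 has no row below 14 or above 67. Below 14 the formula exceeds the screening value: f(10) = 14 − 1.33 = 12.67.

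**The case against.** The best defence is that renewed quit attempts are allowed throughout. A participant may have quit again the night before session 13, and if abstinent at Week-6 means only not smoking now, an overnight limit is coherent. A lower cut-off might reject such a person. This stands for that reading of Week-6, which Hypothesis 3 leaves open. It does not rescue the rule for the 7- and 30-day outcomes, because someone who quit last night does not meet them.

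Also fair: CO only checks a self-report, so harm requires a false one; visit pay is not tied to abstinence; and cotinine supplements CO at six months. Scaling the limit to each participant's screening CO is a deliberate choice and not a fault in itself.

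A reader might infer that Hypothesis 3 is biased in favour of the combined treatment. The documents do not support that. Both arms use the same rule, the planned regression is on group, and the verification standard behind the published usual-care rates is not given. If those rates rest on self-report alone, this plan is the stricter of the two. A reader might also want to calculate how far the limit should fall with each day since quitting; nothing in the documents supplies such a rate.

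**Conclusion.** The point holds as a defect in the outcome definition and should be fixed. Table 1 is the only CO threshold for validating abstinence. Its label restricts it to the morning after one night, and the text applies it at all later visits. On any reading of the inequality, later visits confirm self-reported abstainers at up to 19–20 ppm (screening CO 30), 29–30 ppm (60) and 31–33 ppm (67).

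The text gap is certain. The link to Week-6 is probable: it assumes that Week-6 counts from the quit date and that the outcome is CO-verified, neither of which is stated. Any false confirmation raises the measured abstinence rate. The number of participants affected cannot be estimated, since the documents give neither a false-report rate nor a distribution of screening CO. The effect on the comparison with published usual care has no known direction. Hypotheses 1 and 2 are not affected.

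**What to change.** Confine Table 1 to the morning-after-quit check, and list that check in Table 2.

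For all later visits, verify the 7-day, 30-day and Week-6 outcomes with one fixed CO cut-off for every participant, no higher than the formula's own constant of 14 ppm. The laboratory should justify the value, and it should be fixed before outcomes are classified. The documents support no particular lower figure. At 14 itself, anyone screened at 14 or below would pass with no fall, so the laboratory should weigh that.

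Report Week-6 results under both rules, with the number of participants reclassified. If outcomes have already been classified, keep Table 1 and add the fixed cut-off as a sensitivity analysis.

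In the same edit, state the inequality so that table and formula agree, give the rule for screening CO below 14 or above 67 ppm, anchor Week-6 to the quit date if that is meant, and say whether it is CO-verified.

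The cost is about a paragraph of text and one row in Table 2; the later-visit breath samples are already planned. Reported quit rates may be lower, and the Hypothesis 3 comparison becomes less like-for-like if the published data used a looser criterion. Reporting both rules covers that.

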## Screening Session

Potential participants will complete a phone screen to determine whether they might be eligible for the study. Remaining potential participants will be scheduled for a full screening session, lasting approximately 5 hours total (30 minutes consent; 4.5 hours study procedures). For the screening session, participants will meet a member of the research team at the Nicotine Research Laboratory at the Durham VA. The study will be explained in detail, and the participants will provide informed consent.

As indicated in the informed consent form and HIPAA authorization, the following information will be collected: Name; address; phone number; age; birth date; social security number; dates of study visits; dates of traumatic events; current health and mental health conditions; alcohol/drug abuse current status and history; medical history information; current medications; smoking status; number of cigarettes smoked per day; pregnancy; traumatic event; veteran status; lab results (saliva analysis, urine drug screen, pregnancy screen); questionnaires; structured clinical interviews; descriptions of traumatic life events; medical chart review, and traumatic data collected at each session during study participation.

Urine samples will be collected for drug screen urinalysis and will be disposed after we obtain the urinalysis chemistry report. Urine drug screens will be used to corroborate self-report of substance use; the presence of substance use disorders is determined by clinical interview (see below). The participant will then provide a breath sample in order to assess CO level and a saliva sample for assessing salivary cotinine, a metabolite of nicotine. Study staff will measure the participant's height and weight in order to

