After saliva samples are returned to the research laboratory, they will be sent for analysis to the University of California at San Francisco Pharmacology Laboratory for analysis. Should this laboratory discontinue salivary assay analysis, or should the PI determine use of another lab is warranted for this purpose, another lab will be identified to provide this service and this new lab will be reported to the IRB. Coded samples will be sent by trained study team members in accordance with the standards of practice outlined in Research Transporting and Shipping Biological Specimens, SRS SOP 202. Saliva samples will be analyzed for the presence of cotinine using a standard cut point off 10 ng/ml to determine abstinence. A blind sample of 5% will be run again to assure test accuracy of saliva samples. Secondary smoking outcomes will include 7-and 30-day point prevalence abstinence at each assessment, where abstinence is defined as no tobacco use in the prior 7 or 30 days respectively (McFall et al., 2010)

Any participant who is unable to remain abstinent from smoking after their quit date will be encouraged to make additional quit attempts. Participants will be allowed to make as many quit attempts as necessary during their study enrollment until they are successful or until they have completed their study enrollment. There will be no additional sessions provided for those participants who do not remain abstinent.

Consistent with guidelines for Integrated Care for Smoking Cessation, participants will continue to receive brief care for smoking cessation for as long as they remain in therapy for PTSD. In the CPT-C and smoking condition, this means that study session 8 will be the first session of smoking cessation counseling that will focus on relapse prevention and encouraging those who have relapsed to make an additional attempt to stop smoking. In sessions 8-13, participants will complete questionnaires to assess psychiatric symptoms and smoking variables and continue to receive smoking cessation follow-up counseling. In the smoking cessation condition, participants will complete the six sessions included in the Integrated Care for Smoking Cessation manual, as well as completing brief smoking counseling when completing assessments at study sessions following the quit attempt.

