## Relapse

All participants will complete the intervention protocol, regardless of smoking relapse. Participants who relapse will have the option of completing the intervention so they can continue to apply smoking cessation skills to subsequent quit attempts. Once the intervention and smoking protocol is completed, participants who relapse will be encouraged to make additional quit attempts until the end of the study at the 6-month follow-up appointment. Relapse will be defined as smoking at least 5 cigarettes a day for 3 consecutive days.

In the follow-up session, if a participant reports an inability to attain or maintain abstinence, we will utilize the Timeline Followback (TLFB) method, which was designed by National Institute on Alcohol Abuse and Alcoholism (NIAAA) to retrospectively evaluate substance use. In this interview, which will last approximately 15 minutes, participants will provide retrospective estimates of their smoking behavior over the time period since their participation. This information will be used to evaluate smoking rates post-quit and relapse incidence among the sample.

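### At six months, abstinence is judged by salivary cotinine with no rule for participants on permitted restarted NRT, or for a CO pass with a cotinine fail

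*Combined protocol and SAP*

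**What the plan says.** Four parts of the combined protocol and SAP bear on this.

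- **The test.** Assessments After Screening verifies self-reported abstinence by breath CO at laboratory visits after the quit date, against limits scaled to each participant's screening CO (Table 1). It then adds: "At the six month follow-up visit, salivary cotinine will also be used to confirm self-reported" abstinence. The cut point follows: "Saliva samples will be analyzed for the presence of cotinine using a standard cut point off 10 ng/ml to determine abstinence".
- **What the test measures.** Screening Session describes "salivary cotinine, a metabolite of nicotine".
- **What abstinence means.** The 7-day and 30-day point-prevalence outcomes are scored at each assessment, "where abstinence is defined as no tobacco use in the prior 7 or 30 days respectively".
- **When NRT may be in use.** Nicotine Replacement Therapy sets the scheduled end: "All NRT, including both the patch and rescue method, will end 6 weeks after the target quit-smoking date". It then says that a participant who has not stayed abstinent during follow-up is someone of whom "he/she may be allowed to reinitiate NRT during the follow-up period in order to make a renewed quit attempt". The Relapse section says that those who relapse will be "encouraged to make additional quit attempts until the end of the study at the 6-month follow-up appointment".

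Under Data Analysis and Hypotheses, the smoking analysis for Hypothesis 3 is abstinence at Week 6. Cessation at six months is a secondary, exploratory look.

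**The concern.** The definition and the test concern different things. The definition asks about tobacco; the test responds to nicotine. While no participant is on NRT this does no harm. Once restarted NRT is permitted, a participant who meets the definition may fail the test, and nothing in the plan exempts NRT users or says which marker prevails when the two disagree.

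Any resulting error runs one way: it removes real abstainers from the six-month count. Because NRT is restarted only after failure to stay abstinent, the error falls on those who lapsed and then quit again. Hypothesis 3 is worded as a comparison with published usual-care figures. If the six-month rate is used in that comparison, a loss that is equal in both arms would still understate the combined arm, unless the published figures were verified in the same way, which the plan does not say.

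**Working it through.** The plan states no abstinence rate, restart rate or cotinine level under NRT, so there is no figure of its own to reproduce. The check has two parts.

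**1. Can the two rules meet in one participant?**

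- Scheduled NRT ends 6 weeks after the quit date. Taking six months as 26 weeks, that leaves 26 − 6 = 20 NRT-free weeks before session 15. For participants who follow the schedule there is no conflict.
- The restart provision reopens NRT during follow-up without an end date or a gap before session 15. A restarted course can therefore still be running at that visit, or have just ended.
- Neither Table 2's tasks for session 15 nor the measures listed under Assessments After Screening include a question on current NRT use.
- CO is measured at the same visit, but cotinine is an added confirmation and no rule covers disagreement.

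So the conflict can arise, and the plan does not resolve it. After screening, cotinine is named only for the six-month visit, so the Week-6 analysis is not touched.

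**2. How large might it be? (illustration on assumed values)**

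Inputs:

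- n per arm: 25 (the enrollment goal of at least 50, halved) or 35 (the 70 to be recruited, halved). Equal allocation is an assumption.
- p, true six-month abstinence: 20%, assumed.
- f, the share of true abstainers on NRT at the visit: 10%, 20% or 40%, assumed.
- Everyone on NRT is taken to exceed 10 ng/ml. This is also assumed, and is the worst case.

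Observed rate = p × (1 − f). Abstainers lost per arm = n × p × f, where n × p is 25 × 0.20 = 5 or 35 × 0.20 = 7.

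| f | Observed rate | Lost, n = 25 | Lost, n = 35 |
|---|---|---|---|
| 10% | 0.20 × 0.90 = 18% | 5 × 0.10 = 0.5 | 7 × 0.10 = 0.7 |
| 20% | 0.20 × 0.80 = 16% | 5 × 0.20 = 1.0 | 7 × 0.20 = 1.4 |
| 40% | 0.20 × 0.60 = 12% | 5 × 0.40 = 2.0 | 7 × 0.40 = 2.8 |

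Over a wider assumed range (p from 10% to 30%, f from 10% to 50%), the loss runs from 0.10 × 0.10 = 1 point to 0.30 × 0.50 = 15 points. That is 0.25 to 3.75 people in an arm of 25.

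Unequal restart: if f were 10% in one arm and 40% in the other, equal true rates of 20% would appear as 18% and 12%, a gap of 6 points. With 25 per arm that is 25 × 0.06 = 1.5 people. The standard error of a difference at 20% is √(2 × 0.20 × 0.80 / 25) = 0.113, about 11 points, so the gap is 0.06 / 0.113 ≈ 0.5 standard errors.

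**The case against.** The strongest reply is that few people can be affected. A participant must fail to stay abstinent, be allowed NRT again, stop smoking again, and still be on NRT or just off it at session 15. The restart is discretionary, and it is quit attempts, not NRT, that the Relapse section encourages. This stands, and it is why the number is probably small.

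A second reply is that cotinine only supplements self-report and CO, so a sensible analyst would not fail an NRT user on cotinine alone. That may be so. But the cut point is said to determine abstinence, and nothing written allows CO to prevail. The choice would be made after the data are seen.

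A third reply is that NRT use could be recovered. The study physician sets the dosage of any restart, and participants are asked about side effects at sessions after NRT begins. This stands in part: records probably exist, but neither source is a planned record of use, with dates, at session 15.

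A reader might go further and infer that non-smokers on NRT will be counted as smokers. The documents do not support that: they give no cotinine level by product, dose or time since last use. A reader might also infer a false difference between the arms. The 6-point example needs a four-fold imbalance in f that nothing in the documents suggests, and even then it amounts to 1.5 people.

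**Conclusion.** The point holds in a limited form. At six months the stated test can reject participants who meet the stated definition, and the plan has no rule for NRT users or for a CO pass with a cotinine fail. What is certain is the missing rule. How many people it would misclassify is not known: the illustration of 0.5 to 2 lost per arm of 25 rests on an assumed 20% abstinence, assumed NRT shares of 10% to 40%, equal allocation, and cotinine above the cut point in every NRT user.

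It would be wrong to read this as undermining the trial's main results. Hypotheses 1 and 2 concern PTSD and depressive symptoms, and the Week-6 smoking analysis does not use cotinine. The secondary six-month analysis and point prevalence at that visit are exposed. The plan should be corrected before six-month abstinence is classified, but this is not a critical fault.

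**What to change.** Add to the six-month procedures and the abstinence definition:

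1. Record current and recent NRT use, with dates, at session 15, and define the recent period in advance.
2. For those users, a cotinine value above 10 ng/ml does not by itself reclassify self-reported abstinence that CO confirms. For everyone else the cotinine rule stays as it is.
3. Report the number of NRT users by arm.
4. Give two sensitivity analyses: the cotinine-only classification for all participants, and a classification of NRT users with a CO limit stricter than Table 1, fixed in advance.

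The cost is one question and a short definition, with no new sample or visit. The drawback is weaker verification for NRT users. CO covers a shorter window than cotinine. Table 1's limits are labelled for overnight abstinence, run from 15 to 33, and are lenient: a screening CO of 28 to 30, for example, passes at 20. Some false negatives could thus be exchanged for false positives in the same group, which is the reason for the stricter-CO analysis. Nothing here implies a change to how NRT is provided.
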